11.2 Diarrhea/Colitis

Diarrhea and colitis were also seen frequently. Median time to onset was 4 months, with the majority of cases occurring before 8 months, and symptoms could be prolonged (median duration 0.5 months). For grade 1-2 diarrhea or asymptomatic colitis, initiate supportive care with antidiarrheal agents, continue medication and monitor weekly until resolution. If unresponsive to antidiarrheals then duvelisib should be held and enteric steroids such as budesonide should be started. Duvelisib may then be restarted at a reduced dose as deemed clinically appropriate by the treating physician.

For subjects with abdominal pain, stools with mucus or blood, or severe diarrhea, hold duvelisib and start systemic or enteric steroids. If possible, a colonoscopy and work-up for immune-mediated colitis should be performed. Restart duvelisib at a reduced dose upon resolution of symptoms to less than or equal to CTCAE Grade 1. For recurrent events, duvelisib should be permanently discontinued.

11.3 Cutaneous Reactions

Cutaneous reactions including drug reaction with eosinophilia and systemic symptoms (DRESS) and toxic epidermal necrolysis (TEN) occurred with duvelisib. Median time to onset was 3 months with a median event duration of 1 month. Patients often presented with pruritic, erythematous or maculo-papular rash. Subjects should report rashes, sores, ulcers on skin, lips, mouth, blisters, rash, fevers promptly. Subjects with Grade 1-2 reactions should continue duvelisib at the current dose, supported with

emollients, anti-histamines, topical steroids and close monitoring. If reaction is more severe, duvelisib should be held, and steroids (topical and systemic) and antihistamines should be given. Patients should be monitored at least weekly. Duvelisib should be discontinued if cutaneous reactions recur. If subjects experience, SJS, TEN, or DRESS of any grade, discontinue duvelisib.

11.4 Pneumonitis

Serious cases of pneumonitis occurred with duvelisib. Median time to onset of any grade was 4 months with the majority of cases occurring prior to 9 months and with a mean duration of event of 1 month. Subjects should report new cough or shortness of breath. Patients who have pulmonary signs and symptoms such as cough, dyspnea, hypoxia, radiologic changes, or decline of >5% in oxygen saturation should have duvelisib held and be evaluated. Infectious etiologies should be treated as above. Systemic steroids should be considered. For moderate disease, reduced duvelisib doses can be considered. If non-infectious pneumonitis recurs or does not respond to steroid therapy, discontinue duvelisib. For severe or life-threatening pulmonary disease, duvelisib should be permanently discontinued.

11.5 Neutropenia

Patients with hematologic conditions treated with duvelisib frequently developed neutropenia. CBC with differential should be checked at least every 2 weeks during cycle 1, and more frequently for those with ANC < 1000 cells/ μ L. Withhold duvelisib if ANC < 500 cells/ μ L, monitor weekly and resume at same dose of the first occurrence or at a decreased dose for subsequent occurrence. Duvelisib can be resumed when ANC > 100 is reached in the absence of signs of infection. G-CSF may be used per ASCO guidelines.

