Neutropenia	Absolute neutrophil count (ANC) 500 to 1000 cells/µL	
Duvelisib
 
 - Maintain duvelisib dose - Monitor ANC at least weekly 
Nivolumab
 
 - Withhold nivolumab until resolved if it is felt to contribute to the neutropenia, and otherwise continue nivolumab as previously - Resume at same dose
	ANC less than 500 cells/µL	
Duvelisib
 
 - Withhold duvelisib

Toxicity	Adverse Reaction Grade	Recommended Management
		
 - Monitor ANC until > 500 cell/uL - Resume duvelisib at same dose (first occurrence) or at a reduced dose for subsequent occurrence 
Nivolumab
 
 - Withhold nivolumab until resolved if it is felt to contribute to the neutropenia, and otherwise continue nivolumab as previously - Resume at same dose 
*If concern for auto-immune neutropenia, then hold nivolumab and follow practice guidelines

Thrombocytopenia	Platelet count 25K to < 50K cells/ μ L (Grade 3) with Grade 1 bleeding	
Duvelisib
 
 - No change in dose - Monitor platelet counts at least weekly 
Nivolumab
 
 - Withhold nivolumab until resolved - Resume at same dose
	Platelet count 25K to < 50K cells/ μ L with grade 2 bleeding OR platelet count <25K cells/ μ L (Grade 4)	
Duvelisib
 
 - Withhold duvelisib - Monitor platelet count until > 25K cells/uL and resolution of bleeding if applicable. - Resume duvelisib at same dose (first occurrence) or resume at a reduced dose for subsequent occurrence 
Nivolumab
 
 - Withhold nivolumab until resolved - Resume at same dose 
*If concerned for autoimmune thrombocytopenia, hold nivolumab and follow practice guidelines

Table 7.7 Dose Reductions for Duvelisib

Initial Dose	Decreased Dose
15mg Daily	None

25mg Daily	15mg Daily
25mg BID	25mg Daily

Note: If patient is on dose level 1, 15mg daily and has a dose interruption, duvelisib will be resumed at same dose. If patient subsequently requires another dose interruption at this level for the same toxicity, duvelisib should be discontinued. No more than 2 dose reductions for the same side effect are allowed for any patient, irrespective of starting dose.

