11.0 Management of Adverse Events with Duvelisib

Management of adverse events often depends on clinical context. From prior experience, suggestions regarding duvelisib toxicities are below per product insert and investigator's brochure. Please refer to section 7.6 for information on managing AEs with nivolumab and duvelisib. Please also refer to published guidelines from ASCO for management of immune-related adverse events²³.

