# pills/caps/tabs that should have been taken:	
Discrepancy Notes:	

SUMMARY OF CHANGES

Protocol dated 4-27-22

Page 1	Version date changed from 3-11-22 to 4-27-22
Page 1 - 2	Removed references to Emory University
Page 8	Table ii. Protocol Summary, Methodology, Removed "multi-center"
Page 8	Table ii. Protocol Summary, Removed reference to Emory Winship Cancer Institute
Page 14	Section 3.1, General Study Design, Removed "multi-center study to be conducted at Winship Cancer Institute at Emory University"
Page 17	Section 4.2, Exclusion Criteria, 1 st bullet, Removed "with"
Page 20	Section 4.3, Subject Recruitment, 1 st sentence, Removed "Emory Winship Cancer Institute"
Page 23	Section 5.4, Procedure for Registration of Subjects, Removed "Winship Cancer Institute of Emory University;"
Page 22	Section 5.1, Study Site, Removed "Winship Cancer Institute"
Page 28	Section 7.4.1, Receipt of Drug Supplies, Removed "Winship Cancer Institute"
Page 30	Table 7.6, Dose Adjustments for Toxicity, Updated recommended management for Neutropenia
Page 37	Section 7.7, Removed references to Emory

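### Section 11.5 allows duvelisib to restart at ANC above 100, inside the range where the same section and Table 7.6 withhold it

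*Combined protocol and SAP*

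**What the plan says.** **Neutropenia, Section 11.5.** The hold rule is "Withhold duvelisib if ANC < 500" cells/µL, with weekly monitoring, the same dose after a first occurrence and a lower dose after later ones. The next sentence gives the restart condition: "Duvelisib can be resumed when ANC > 100 is reached in the absence of signs of infection". No unit is attached to the 100.

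**Neutropenia, Table 7.6.** In the row "Absolute neutrophil count (ANC) 500 to 1000" cells/µL the duvelisib dose is maintained. Below 500 duvelisib is withheld, with the instruction "Monitor ANC until > 500 cell/uL", followed by "Resume duvelisib at same dose (first occurrence) or at a reduced dose for subsequent occurrence".

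**How the two sections relate.** Section 11.0 says that "suggestions regarding duvelisib toxicities are below per product insert" and the investigator's brochure, and adds "Please refer to section 7.6 for information on managing AEs with nivolumab and duvelisib".

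**Strong CYP3A inhibitors, Section 7.10.1.** These are to be avoided. If one is unavoidable, the investigator may allow duvelisib to be reduced to 15 mg twice daily. The clause does not mention the patient's dose level. The levels in Section 14.1.1 are 15 mg daily, 25 mg daily and 25 mg twice daily. Table 7.7 steps 25 mg daily down to 15 mg daily and has no step below 15 mg daily.

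**Duration.** The Protocol Summary runs treatment to progression, unacceptable toxicity or one year, taking the longer. Section 4.4.1 (Termination of Study Participation) ends treatment as soon as any listed criterion is met, including progression, unacceptable adverse events and completion of 12 months.

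**The concern.** A restart threshold has to sit at or above the threshold for holding the drug, or the hold has no effect. In Section 11.5 it sits below. A patient held at an ANC of 300 without signs of infection already meets the restart condition on the day of the hold. Read literally, the hold binds only at an ANC of 100 or less, or when infection is evident.

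The protocol itself gives reason to take this seriously. Section 11.5 notes frequent neutropenia in haematology patients on duvelisib, and Section 11.1 cites a boxed warning for infection.

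The CYP3A clause raises a smaller issue. At the two lower dose levels the only dose it offers is not a reduction, so the clinician is left with avoidance or discretion. Section 7.5 suggests that a dose below 25 mg twice daily may prove best. If the recommended phase II dose is one of the lower levels, the clause could not work as a reduction for the expansion patients treated at it.

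**Working it through.** No design figure is involved, so the check compares current passages and uses simple arithmetic.

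**(a) Neutropenia.** The 100 in Section 11.5 is taken to be in cells/µL, as in the sentences around it.

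| ANC (cells/µL) | Section 11.5 | Table 7.6 |
|---|---|---|
| 100 or below | withhold | withhold |
| 101–499 | withhold, and may resume if no signs of infection | withhold |
| above 500, up to 1000 | no hold | maintain; a held patient may resume |

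- Overlap of the hold rule (below 500) with the restart rule (above 100): ANC 101 to 499.
- Restart threshold relative to the hold threshold in 11.5, and to the recovery threshold in Table 7.6: 100 / 500 = 0.2.
- With the restart threshold in 11.5 set above 500, no ANC value satisfies both rules and the overlap disappears.

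**(b) CYP3A clause.** 15 mg × 2 = 30 mg/day. Compared with each assigned dose:

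| Level | Assigned dose (mg/day) | 30 mg/day as a ratio |
|---|---|---|
| I: 15 mg daily | 15 | 30/15 = 2.0 |
| II: 25 mg daily | 25 | 30/25 = 1.2 |
| III: 25 mg twice daily | 2 × 25 = 50 | 30/50 = 0.6 |

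Only Level III yields a reduction. The Table 7.7 step for 25 mg daily is 15/25 = 0.6, the same proportional cut, but Section 7.10.1 does not refer to it.

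**(c) Duration.** Taken literally, the summary would continue treatment after progression or toxicity until one year, or beyond one year without progression. Section 4.4.1 rules out both.

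**The case against.** The best reply on (a) is that Section 11 offers suggestions and sends the reader to Section 7.6, where the rule is coherent: maintain at 500 to 1000, withhold below 500, resume above 500. The sentence with 100 is permissive, requires no signs of infection, and contradicts the sentence before it so plainly that a careful clinician would query it. No analysis depends on it.

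This softens the conflict without removing it. No stated rule gives Table 7.6 precedence. Its own management column is headed as recommendations, and Section 7.6 says the table is not exhaustive. Section 11 is also not purely advisory: Section 11.1 makes holding duvelisib mandatory for grade 3 or higher infection. A reader could take the infection condition in 11.5 as extra detail added to the table.

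One part of the objection stands in full. The change log entry "Table 7.6, Dose Adjustments for Toxicity, Updated recommended management for Neutropenia" does not say what was altered, so it cannot show that the figure of 500 is the newer one. The case for 500 rests on its agreement with both hold rules and on the referral from Section 11.0 to Section 7.6.

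On (b), the clause speaks of a reduction, so by its own terms it does not direct anyone to raise a dose. Section 4.2.4 excludes strong inhibitors in the two weeks before treatment, Section 7.10.1 says to avoid them, and dose adjustment is left to the investigator. What remains is a missing instruction for two dose levels. On (c), Section 4.4.1 governs and the summary wording has no operative effect.

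**Conclusion.** The concern holds. Section 11.5 is wrong as written for ANC 101 to 499 cells/µL, with a restart threshold 0.2 times the one in Table 7.6. This is the only part that must be fixed: it is a current dosing threshold that weakens a safety hold, and one number corrects it.

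The CYP3A clause is a lesser drafting fault that should be fixed: 15 mg twice daily is 2.0, 1.2 and 0.6 times the assigned daily dose at Levels I, II and III. The duration wording is editorial.

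The documents give no frequency of ANC below 500 in this population or of strong-inhibitor use on study, so the number of patients affected is unknown. Section 15.0 expects melanoma patients to tolerate duvelisib better than haematology patients did. Whether 500 or 1000 (a dropped zero) was intended in 11.5 cannot be settled from the documents; the conflict exists in either case.

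**What to change.** 1. **Section 11.5 (must fix).** Replace the restart threshold with ANC above 500 cells/µL, including the unit, to match Table 7.6. If the clinical team prefers a higher value, such as 1000, set it in both places.
2. **Section 7.10.1 (should fix).** Limit the 15 mg twice-daily option to patients on 25 mg twice daily. State the action for 25 mg daily (for example 15 mg daily, as in Table 7.7, or hold) and for 15 mg daily (do not co-administer, or hold). The clinical team should choose.
3. **Protocol Summary (editorial).** Change the duration line to say whichever occurs first.

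The cost is one number, one or two sentences and one phrase. Design, sample size, monitoring boundaries and analysis are unchanged.

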12.0 Assessment of Disease

Patients will be evaluated for response every 12 weeks while on study. If clinicians have clinical concerns, evaluation by imaging may be done as there is clinical or subjective evidence of progression before 12 weeks, with imaging resumed on a Q 12-week imaging cycle. Assessments for response and progression will be carried out according to the Response Evaluation Criteria in Solid Tumors (RECIST) guideline version 1.1¹⁹ which are reproduced and paraphrased in the sections below. Following RECIST criteria, changes in the largest diameter of the tumor lesions and the shortest diameter for malignant lymph nodes will be used.

12.1 Definitions

- **Evaluable for toxicity** – All patients are evaluable for toxicity upon initiating treatment of nivolumab and duvelisib. For the phase I portion, patients should have taken 75% of duvelisib pills according to pill diary and pill counts.
- **Evaluable for objective response** – Patients who have measurable disease at baseline and have their disease re-evaluated at 12 weeks of therapy will be evaluable for response. Patients who

exhibit objective disease progression prior to the end of cycle 1 will also be considered evaluable.

- **Evaluable non-target disease response** – Patients who have baseline lesions that are evaluable but do not meet the definitions of measurable disease have received at least one cycle of therapy and have had their disease re-evaluated will be considered evaluable for non-target disease. The response assessment is based on the presence, absence, or unequivocal progression of the lesions.
- **Measurable disease** – Tumor lesions that can be accurately measured by the longest diameter in the plane of measurement with a minimum size of 10mm by CT scan, 10mm caliper measurement on clinical exam, 20mm by chest x-ray. CT scan thickness should be no greater than 5mm. Tumor measurements must be recorded in mm or decimal fractions of centimeters.
- **Malignant lymph nodes** – To be considered pathologically enlarged and measurable, a lymph node must be $\geq 15\text{mm}$ in short axis when measured by CT scan. Only the short axis will be measured and followed.
- **Non-measurable disease** – All other lesions, including small lesions $< 10\text{mm}$ and lymph nodes $< 15\text{mm}$ are considered non-measurable disease. Other non-measurable disease examples include ascites, pleural or pericardial effusion, lymphangitic involvement of skin or lung, abdominal masses/abdominal organomegaly that don't correlate to CT or MRI, bone lesions, inflammatory breast disease.
- **Target lesions** – When more than one measurable lesion is present at baseline all lesions up to a maximum of five lesions total (max two per organ) representative of all involved organs should be recorded and measured at baseline. If only 2 organs are involved, the maximum number of target lesions is four. Target lesions should be selected based on lesions with the longest diameter, be representative of involved organs, and should lend themselves to repeated measurements. If lesions do not fulfill these requirements, the next largest lesion that can reproducibly be measured should be selected.

A sum of the diameters (longest for non-nodal lesions, short axis for nodal lesions) for all target lesions will be calculated and reported as the baseline sum of diameters. If lymph nodes are to be included in the sum, then only the short axis will be added. The baseline sum will be used as a reference to further characterize any objective tumor regression in the measurable dimension of the disease.

- **Non-target lesions** – All other lesions or sites of disease including pathological lymph nodes should be identified as non-target lesions and should also be recorded at baseline. Measurements are not required and these lesions should be followed as present, absent or unequivocal progression.

Other considerations

- Lesions that meet radiographic criteria for simple cysts should not be considered malignant lesions, because they are, by definition, simple cysts. Cystic lesions thought to represent cystic metastases can be considered as measurable lesions, if they meet the definition of

measurability described above. However, if non-cystic lesions are present in the same patient, they are preferred for selection as target lesions.

- Lesions situated in a previously irradiated area, or an area subjected to other loco-regional therapy, are usually considered non-measurable unless there has been demonstrated progression in the lesion.

12.2 Methods for Evaluation of Measurable Disease

All measurements should be taken and recorded in the metric system using ruler or calipers. All baseline evaluations should be performed as closely as possible to the beginning of treatment and never more than 4 weeks before the beginning of the treatment. The same method of assessment and the same technique should be used to characterize each identified and reported lesion at baseline and during follow-up. Imaging-based evaluation is preferred to evaluation by clinical examination unless the lesion(s) being followed cannot be imaged but are assessable by clinical exam.

- Clinical lesions - Clinical lesions will only be considered measurable when they are superficial (e.g., skin nodules and palpable lymph nodes) and ≥ 10 mm (≥ 1 cm) diameter as assessed using calipers (e.g., skin nodules). In the case of skin lesions, documentation by color photography, including a ruler to estimate the size of the lesion, is recommended.
- Conventional CT and MRI – CT is the preferred modality for evaluating lesions. By RECIST, the measurability of lesions on CT scan based on the assumption that CT slice thickness is 5 mm (0.5 cm) or less. If CT scans have slice thickness greater than 5 mm (0.5 cm), the minimum size for a measurable lesion should be twice the slice thickness. MRI is also acceptable in certain situations (e.g. for body scans).

MRI has excellent contrast, spatial, and temporal resolution; however, there are many image acquisition variables involved in MRI, which greatly impact image quality, lesion conspicuity, and measurement. As with CT, if an MRI is performed, the technical specifications of the scanning sequences used should be optimized for the evaluation of the type and site of disease.

Furthermore, as with CT, the modality used at follow-up should be the same as was used at baseline and the lesions should be measured/assessed on the same pulse sequence. Ideally, the same type of scanner should be used and the same image acquisition protocol should be followed as closely as possible across all scans. Body scans should be performed with breath-hold scanning techniques, if possible.

- PET-CT - The low dose or attenuation correction CT portion of a combined PET-CT is not always of optimal diagnostic CT quality for use with RECIST measurements. However, if the site can document that the CT performed as part of a PET-CT is of sufficiently comparable diagnostic quality to a diagnostic CT (with IV and oral contrast), then the CT portion of the PET-CT can be used for RECIST measurements and can be used interchangeably with conventional CT in accurately measuring cancer lesions over time.

- FDG-PET - While FDG-PET response assessments need additional study, it is sometimes reasonable to incorporate the use of FDG-PET scanning to complement CT scanning in assessment of progression (particularly possible 'new' disease). New lesions on the basis of FDG-PET imaging can be identified according to the following algorithm:
 - Negative FDG-PET at baseline, with a positive FDG-PET at follow-up is a sign of PD based on a new lesion.
 - No FDG-PET at baseline and a positive FDG-PET at follow-up: If the positive FDG-PET at follow-up corresponds to a new site of disease confirmed by CT, this is PD. If the positive FDG-PET at follow-up is not confirmed as a new site of disease on CT, additional follow-up CT scans are needed to determine if there is truly progression occurring at that site (if so, the date of PD will be the date of the initial abnormal FDG-PET scan). If the positive FDG-PET at follow-up corresponds to a pre-existing site of disease on CT that is not progressing on the basis of the anatomic images, this is not PD.
 - FDG-PET may be used to upgrade a response to a CR in a manner similar to a biopsy in cases where a residual radiographic abnormality is thought to represent fibrosis or scarring. The use of FDG-PET in this circumstance should be prospectively described in the radiographic protocol and supported by disease-specific medical literature for the indication. However, it must be acknowledged that such approaches may lead to false positive CR's due to limitations of FDG-PET resolution/sensitivity.
- Ultrasound – Ultrasound examinations are not reliably reproduced for review and are operator dependent. As such, it cannot be guaranteed that the same techniques and measurements are taken on each evaluation, and ultrasound should not be routinely used as a method of lesion measurement. If new lesions are identified by ultrasound, they should be verified by another modality as described above.
- Cytology and Histology - These techniques can be used to differentiate between partial responses (PR) and complete responses (CR) in rare cases (e.g., residual lesions in tumor types, such as germ cell tumors, where known residual benign tumors can remain). The cytological confirmation of the neoplastic origin of any effusion that appears or worsens during treatment when the measurable tumor has met criteria for response or stable disease is mandatory to differentiate between response or stable disease (an effusion may be a side effect of the treatment) and progressive disease.

